9.2.2.4 Investigation for patients of special interest

The patient who has signed on the data release consent form, patients of special interest (pediatric, geriatric, pregnant women, renal impairment, hepatic impairment and other special population) among the patients who conducted investigation for safety assessment after the administration of Spesolimab IV can be further summarized into subgroups collected from this.

9.2.3 Study visits

9.2.3.1 Visit 1: Baseline

At Visit 1, the informed consent is obtained from the patient using the data release consent form. After obtaining written consent, the following data will be collected.

- Visit date
- Signed date of data release consent
- Information on diagnosis of GPP and flare: date of diagnosis of GPP and this flare, average number of flares per year and family history of psoriasis
- Information on inclusion / exclusion criteria
- Demographics: gender, age (year and month of birth), current pregnancy and breastfeeding status (female only), smoking status, alcohol intake status
- Medical history: within 6 months
- Past / concomitant medications or non-drug therapy: within 6 months
- Physical examination: blood pressure, pulse rate, weight, height, body temperature
- GPPGA pustulation sub-score
- GPPGA score
- GPPASI (if available)
- Pain VAS (if available)
- PSS (if available)
- IL-36RN mutation status (if available)
- C-reactive protein (CRP) level (if available)
- Other laboratory test results (if available)
- Spesolimab IV administration status: date of administration, total daily dose

At Visit 1, the patient will be requested to contact the investigator in the event of any AEs noted after initiating Spesolimab IV treatment.

9.2.3.2 Visit 2: 1 week from Visit 1

After 1 week from Visit 1, the patient returns for follow-up. The following data will be collected.

- Visit date
- Physical examination: blood pressure, pulse rate, body temperature
- Concomitant medications or non-drug therapy
- Any changes in the Spesolimab IV administration status
- Subsequent exposure to subcutaneous Spesolimab
- GPPGA pustulation sub-score
- GPPGA score
- GPPASI (if available)
- CRP level (if available)
- Other laboratory test results (if available)
- Safety assessment: any AEs noted
- Study completion status (if applicable)
- Investigator's overall effectiveness assessment (if applicable)

9.2.3.3 Visit 3: 4 weeks from Visit 1

After 4 weeks from Visit 1, the patient returns for follow-up. The following data will be collected.

- Visit date
- Physical examination: blood pressure, pulse rate, body temperature
- Concomitant medications or non-drug therapy
- Any changes in the Spesolimab IV administration status
- Subsequent exposure to subcutaneous Spesolimab
- GPPGA pustulation sub-score
- GPPGA score
- GPPASI (if available)
- Pain VAS (if available)
- PSS (if available)
- CRP level (if available)
- Other laboratory test results (if available)
- Safety assessment: any AEs noted
- Study completion status (if applicable)
- Investigator's overall effectiveness assessment (if applicable)

9.2.3.4 Visit 4: 24 weeks from Visit 1

After 24 weeks from Visit 1, the patient returns for a final follow-up. The following data will be collected.

- Visit date
- Any changes in the Spesolimab IV administration status
- Subsequent exposure to subcutaneous Spesolimab
- Safety assessment: any AEs noted
- Concomitant medications or non-drug therapy
- Study completion status

This visit can be conducted by [contact] Flow chart

Data points	Baseline	Follow-up 1	Follow-up 2	Follow-up 3
Visit Number	1	2	3	4
Week/s	0	1	4	24
Data release consent	X			
Diagnosis of GPP and flare ¹⁾	X			
Review of Inclusion / exclusion criteria	X			
Demographics ²⁾	X			
Medical history ³⁾	X			
Physical examination ⁴⁾	X	X	X	X
Past / concomitant medicatons or non-drug therapy ⁵⁾	X	X	X	X
Spesolimab IV administration status	X	X*	X**	X**
Supsequent exposure to subcutaneous spesolimab		X	X	X
GPPGA pustulation sub-score	X	X	X	

Data points	Baseline	Follow-up 1	Follow-up 2	Follow-up 3
Visit Number	1	2	3	4
Week/s	0	1	4	24
GPPGA score	X	X	X	
GPPASI	X ^A	X ^A	X ^A	
Pain VAS	X ^A		X ^A	
PSS	X ^A		X ^A	
CRP level	X ^A	X ^A	X ^A	
IL-36RN mutation status	X ^A			
Laboratory tests	X ^A	X ^A	X ^A	X ^A
AEs		X	X	X
Investigator's overall effectiveness assessment		X ^B	X	
Study completion		X ^B	X ^B	X

* If flare symptoms persist, an additional 900mg dose may be administered 1 week after the initial dose.

** Any changes to the Spesolimab IV administration status are collected.

^A If collected

^B If applicable

¹⁾ Date of diagnosis of GPP and this flare, average number of flares per year and family history of psoriasis

²⁾ Gender, age (year and month of birth), current pregnancy and breastfeeding status (female only), smoking status, alcohol intake status

³⁾ Within 6 months

⁴⁾ Blood pressure, pulse rate, weight (at V1 only), height (at V1 only), body temperature

⁵⁾ Within 6 months

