9.7.1.2 Number of cases to safety assessment

These include those who signed the data release consent form to participate in this study, took Spesolimab IV once at least, and were followed up by the investigator once or more.

Based on the MFDS guideline, the cases below shall be excluded from safety analysis (defined below):

- a. Patients who did not signed (signature missing), or patients who signed on the data release consent form prior to the contract date
- b. Patients who took Spesolimab IV prior to the contract date
- c. Patients who took Spesolimab IV prior to signing the data release consent form
- d. Patients who have not taken Spesolimab IV
- e. Patients who do not meet the inclusion/exclusion criteria
- f. Follow-up failure: Patients whose safety information cannot be obtained due to lost-to-follow-up
- g. Patients who were prescribed Spesolimab IV for indications outside the local label

However, cases enrolled during the complete enumeration period within 2 years of product launch will be included in the safety set even if the patients who took Spesolimab IV prior to the contract date or prior to signing the data release consent form.

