9.7.1.3 Number of cases to effectiveness assessment

These cases include those who signed the data release consent form to participate in this study, visited as per the study schedule, took Spesolimab IV, and were evaluated for the effectiveness.

Based on the MFDS guideline, the cases below shall be excluded from effectiveness analysis (defined below):

- a. Patients excluded from the safety analysis set listed in section [9.7.1.3](#).
- b. Patients missing information of effectiveness assessment listed in section [9.3.2.2](#).

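### Week 1 and Week 4 are counted from the consent visit and no pre-infusion baseline is required, so enumeration patients infused before consent can have mistimed responses and, unless a pre-dose score is abstracted, a post-treatment baseline

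*Protocol*

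**What the plan says.** Protocol Section 9.2.3.1 makes Visit 1 both the consent visit and the baseline: "At Visit 1, the informed consent is obtained from the patient using the data release consent form". It continues: "After obtaining written consent, the following data will be collected". The list that follows holds the GPPGA and its pustulation sub-score and, if available, GPPASI, pain VAS and PSS. It also holds the infusion date ("Spesolimab IV administration status: date of administration, total daily dose").

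The follow-up visits run from Visit 1. For Visit 2: "After 1 week from Visit 1, the patient returns for follow-up". For Visit 3: "After 4 weeks from Visit 1, the patient returns for follow-up". Visit 4 is set at 24 weeks on the same clock. The possible second dose has a different origin; the flow chart footnote says "an additional 900mg dose may be administered 1 week after the initial dose".

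Section 9.7.1.2 normally excludes from the safety analysis patients treated before contract (item b) or before consent (item c). For the two-year complete-enumeration period it lifts both items. Such cases are "included in the safety set even if the patients who took Spesolimab IV prior to the contract date or prior to signing" the consent form.

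Section 9.7.1.3 then drops two groups from the effectiveness set: "Patients excluded from the safety analysis set listed in section" 9.7.1.3 (the section cites itself, although the list stands in 9.7.1.2), and patients with missing effectiveness data.

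**The concern.** The infusion date is recorded but anchors no visit. For a patient who is infused and consents at the same visit this is harmless. For a patient infused earlier, whom Section 9.7.1.2 deliberately retains, the study clock starts after treatment did.

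Two kinds of result are exposed, in different ways:

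- **The four secondary outcomes** (Section 9.3.2.2) are absolute states at Week 1 and Week 4: pustulation sub-score 0, and GPPGA 0 or 1. They use no baseline value, but they would be read later after infusion than their label says, and possibly after two doses.
- **Change-based results** also depend on the starting value. These are GPPASI 50/75, percent reduction in GPPASI, change in pain VAS and PSS (Section 9.3.2.3), and the paired t-tests (Section 9.7.3). With a treated starting value they would tend to understate improvement.

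A pooled figure would then mix different times since treatment. Effectiveness is the stated secondary objective, and Section 7 says the surveillance results are reflected in the approved information.

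**Working it through.** There is no plan figure to reproduce: the target of 21 rests on prevalence and market conditions (Section 9.5). The check is a reading of the sections together, followed by simple arithmetic.

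**1. Can a patient infused before Visit 1 reach the effectiveness set?**

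- Items b and c of the exclusion list in 9.7.1.2 are lifted for enumeration cases. Item a, consent signed before the contract date, is not lifted. So a patient treated before the contract must also have been treated before consent.
- Item (a) of 9.7.1.3 removes patients excluded from the safety set. These patients are not excluded from it.
- Item (b) removes patients without effectiveness data. A patient scored at Visits 2 and 3 has data.
- The requirement to have attended on schedule does not screen them out, because the schedule itself runs from Visit 1.

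On the plain reading they enter. The faulty cross-reference leaves some doubt.

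**2. Days since first infusion.** Let d be the days from first infusion to Visit 1 (assumed; not in the protocol). Visit 1 is on day d, nominal Week 1 on day 7 + d, nominal Week 4 on day 28 + d. A second dose, if given a week after the first, is on day 7.

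| d | Visit 1 | Week 1 | Week 4 | Second dose, if given |
|---|---|---|---|---|
| 0 | 0 | 7 | 28 | same day as Visit 2 |
| 3 | 3 | 10 | 31 | between Visits 1 and 2 |
| 7 | 7 | 14 | 35 | same day as Visit 1 |
| 14 | 14 | 21 | 42 | before Visit 1 |
| 28 | 28 | 35 | 56 | before Visit 1 |

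For any d above 0 the second dose precedes the nominal Week 1 score.

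**3. Effect on mean change.** Let k of n = 21 patients have a post-treatment baseline, and let r be the share of their improvement already reached at Visit 1. If all patients improve equally by the follow-up score, the mean change shrinks by (k/n) × r. Both k and r are assumptions.

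| k | r = 0.25 | r = 0.50 | r = 0.75 |
|---|---|---|---|
| 3 | 3.6% | 7.1% | 10.7% |
| 7 | 8.3% | 16.7% | 25.0% |
| 10 | 11.9% | 23.8% | 35.7% |

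For one patient with assumed GPPASI of 30 before infusion, 14 at Visit 1 and 8 at Week 4, the reduction is (30 − 8)/30 = 73.3% from the pre-infusion value and (14 − 8)/14 = 42.9% from the Visit 1 value. GPPASI 50 is met in the first case and not in the second.

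**4. Effect on the Week 1 response rate.** The shift is (k/n) × (p_late − p_7), where p_7 is the response probability at day 7 and p_late that at day 7 + d. Assume p_7 = 0.5 and p_late = 0.6 to 0.8. Then k = 3 gives 1.4 to 4.3 percentage points, k = 7 gives 3.3 to 10.0, and k = 10 gives 4.8 to 14.3. The shift is upward only if response keeps rising over that interval.

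**5. After the fix.** With the first infusion as origin and a pre-infusion baseline, d = 0 by definition and the shrinkage in step 3 is zero.

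**The case against.** The best defence is that the form signed at Visit 1 releases data, and the data source is the medical record (Sections 4 and 9.10.2.1). The Visit 1 list includes retrospective items such as six months of medical history. Collecting data after consent can therefore mean entering them from the chart, including a score noted before infusion. This stands. A reader might infer that every such patient's baseline was measured after treatment, and the protocol does not say that. What remains is that nothing asks sites to look for a pre-dose score.

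The flow chart also records drug administration at Week 0 and attaches the second-dose footnote to the Week 1 cell, so Visit 1 is evidently conceived as the treatment-start visit. This stands too. It disposes of the tempting converse, that consent days before infusion would bring Week 1 too early; no text points to such a gap. It does not help patients whom Section 9.7.1.2 retains precisely because treatment came first.

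It can be said that the override names only the safety set and that 9.7.1.3 has its own conditions. That is why entry to the effectiveness set is the plain reading and not a certainty.

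Finally, baseline and window rules are often left to the SAP. That answers part of the remedy, since infusion and visit dates are collected. But the protocol itself fixes the visit anchor, and a SAP cannot recover a pre-dose score that sites were never asked to abstract.

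**Conclusion.** The point holds as a weakness in the time origin and baseline definition, confined to complete-enumeration patients infused before Visit 1. Outside that period item c of 9.7.1.2 removes patients treated before consent. For those who remain, the shift of d days follows directly from the text. The post-treatment baseline is conditional on no pre-dose score being abstracted.

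The overall size is unknown. Each patient is 1/21 = 4.8% of the target, and the ranges above rest wholly on assumed k, r, d and response probabilities. A reader might infer long delays because interim reports begin in April 2024 and data collection in March 2025. The note to the milestones table says the reporting schedule runs from market approval, and the launch date is not given, so those dates do not establish any delay.

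Nor does this route undermine the main result. The primary objective is safety, the effectiveness outcomes are secondary or further, and all analyses are declared exploratory. When adverse event collection starts (Section 11.2) is a separate matter. This should be fixed, but it is not critical.

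**What to change.** - **Section 9.2.3 and the flow chart:** define Week 0 as the date of first Spesolimab IV infusion, and baseline as the last score recorded on or before it. For patients who consent later, ask sites to abstract that score, with its date, from the medical record.
- **Timing:** assign Week 1 and Week 4 assessments by days since first infusion, and flag any score recorded after a second infusion. The window widths can go in the SAP.
- **Section 9.7.1.3:** state whether patients infused before consent belong to the effectiveness set, and correct the reference in item (a). Keep patients without a pre-infusion score in the safety set, but leave them out of the change-from-baseline and GPPASI 50/75 results. Show Week 1 and Week 4 response with and without patients infused before Visit 1.

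The cost is protocol wording, one abstraction request and a derivation rule. Infusion and visit dates are already collected, and no treatment decision changes. The downside is that a few patients drop out of the change-from-baseline results, and some late-consented patients may have no score near day 7 or day 28.

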9.3 VARIABLES

9.3.1 Exposures

Exposure to Spesolimab IV will be estimated as number of doses and time from the first intake date to the last intake date of the patient during the study period.

The recommended dose of Spesolimab IV is a single dose of 900 mg (2 x 450 mg/7.5 ml vials) administered as an intravenous infusion.

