9.3.2.3 Further outcomes

The further outcomes are as follows:

- A GPPASI 75 at Week 4 (if collected)
- A GPPASI 50 at Week 1 (if collected)
- A GPPASI 50 at Week 4 (if collected)
- The percent reduction in GPPASI from baseline at Week 1 (if collected)
- The percent reduction in GPPASI from baseline at Week 4 (if collected)
- Change from baseline in pain VAS score at Week 4 (if collected)
- Change from baseline in PSS score at Week 4 (if collected)
- Investigator's overall effectiveness assessment at Week 1 and/or Week 4

The GPPASI is provided in [Annex 5](#). It is an adaptation for GPP patients of the Psoriasis Area and Severity Index (PASI), an established measure of severity and area of psoriatic lesions in patients with psoriasis [[R96-3541](#)]. Similar adaptations have been used for palmo-plantar psoriasis (PPP) [[R16-3360](#)]. In the GPPASI, the induration component was substituted with the pustules' component. It is a tool that provides a numeric scoring for a patient's overall GPP disease state, ranging from 0 to 72. It is a linear combination of percent of surface area of skin that is affected by erythema, pustules and scaling and the severity of erythema, pustules, and scaling (desquamation) over 4 body regions.

The pain VAS instrument is provided in [Annex 6](#). The pain VAS is a unidimensional measure of pain intensity [[R18-1989](#)]. The respondent is asked to place a vertical (|) mark on the horizontal line to indicate the severity of the pain. Using a ruler, the score is determined by measuring the distance (mm) on the 10-cm line between the "no pain" anchor and the

patient's mark, providing a range of scores from 0–100. A higher score indicates greater pain intensity.

The PSS instrument is provided in [Annex 7](#). The PSS is a 4-item patient-reported outcome (PRO) instrument that was developed to assess the severity of psoriasis symptoms in patients with moderate to severe psoriasis [[R18-1990](#)]. The symptoms included are pain, redness, itching, and burning. Current symptom severity is assessed using a 5-point scale ranging from 0 (none) to 4 (very severe). The symptom scores are added to an unweighted total score (range: 0 to 16).

The overall effectiveness assessment is performed at the investigator's discretion. The information includes:

- Improved: If determined as there is any effect of maintaining or improving symptoms.

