9.3.3 Covariates

- 1) Patient characteristics
 - Demographics: age, gender, current pregnancy status, current breastfeeding status, smoking status, alcohol intake status
 - Physical examination: height, weight, blood pressure, body temperature, pulse rate
 - Disease information: duration of disease, IL-36RN mutation status, medical history, past / concomitant medications or therapies, history and frequency of GPP flares, comorbidities (CV, hepatic or renal impairments, infection, skin diseases (i.e., plaque psoriasis)), family history
- 2) Spesolimab IV administration status: total duration of administration, total administered dose, average daily dose
- 3) Subsequent exposure to subcutaneous Spesolimab: total duration of administration, total administered dose
- 4) Patients of special investigation: pediatric population, geriatric population, pregnant women, lactating women, hepatic impairment, renal impairment
- 5) Laboratory test results
- 6) Others

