9.5 STUDY SIZE

The enrolment target is 21 patients for a total of 6 years, considering the prevalence of generalized pustular psoriasis with acute flares in Korea and the market conditions. [REDACTED] is committed to collecting data from all patients who receive Spesolimab IV within a 2-year period after the product's launch (complete enumeration).

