9.7.3 Effectiveness analysis

Effectiveness analysis will be performed on the effectiveness set.

Effectiveness analyses will be performed by subgroup based on demographics and baseline characteristics.

The standard descriptive statistical parameters (number of patients, mean, standard deviation, median, minimum, maximum, etc.) will be summarized.

The changes of the effectiveness outcomes from baseline will be compared in an exploratory sense via paired t-test.

For investigator's overall effectiveness evaluation, the number and percentage of patients will be presented. If the result of overall evaluation is 'improved', it will be classified as 'effective'. If the result of overall evaluation is 'unchanged' or 'aggravated', it will be classified as 'ineffective'.

'Effective' and 'ineffective' will be reported using numbers of patients, percentages with 95% CIs.

Categorical variable will be reported using numbers of patients, numbers of patients assessed as 'effective', effective rates and 95% CIs. Effectiveness will be analyzed by Pearson's chi-square test or Fisher's exact test to determine if there are statistically significant differences.

Continuous variable will be reported using numbers of patients. Odds ratio and 95% CIs by simple logistic regression will be summarized.

To estimate any factors that are thought to influence an effective rate, logistic regression analysis and/or poisson regression will be conducted, and for statistically significant covariates the meaning will be described.

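### Total dose and duration of Spesolimab IV depend partly on early response, so using them as covariates for the effective rate biases their odds ratios against the second infusion

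*Protocol*

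**What the plan says.** - **Trigger for a second infusion.** The flow chart footnote in 9.2.3.5 reads: "If flare symptoms persist, an additional 900mg dose may be administered 1 week after the initial dose". Re-infusion is discretionary and conditional on the state of the flare.
- **Exposure.** Section 9.3.1: "Exposure to Spesolimab IV will be estimated as number of doses and time from the first intake date to the last intake date", taken over the whole study period.
- **Covariates.** Section 9.3.3(2) lists "Spesolimab IV administration status: total duration of administration, total administered dose, average daily dose". All three become known only after baseline. Number of doses is not in this list, but at 900 mg per infusion total dose carries the same information.
- **Model.** Section 9.7.3: "To estimate any factors that are thought to influence an effective rate, logistic regression analysis and/or poisson regression will be conducted". The subgroup analyses in 9.7.2 and 9.7.3 are tied to demographics and baseline characteristics. The regression sentence has no such limit, and it closes with a rule of interpretation: "for statistically significant covariates the meaning will be described".
- **Outcome.** A patient counts as effective if the investigator's overall evaluation is *improved* (9.7.3). Section 9.3.2.3 places the "overall effectiveness assessment at Week 1 and/or Week 4". The flow chart marks it as if applicable at Week 1 and as scheduled at Week 4.
- **Size.** Section 9.5: "The enrolment target is 21 patients for a total of 6 years".

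**The concern.** A patient reaches 1,800 mg rather than 900 mg because the flare had not settled a week after the first infusion. Patients with two infusions are therefore selected for a poorer early course. When total dose or duration enters a model for the effective rate, that selection is read as an effect of dose. For the Week 4 assessment this is confounding by indication. For a Week 1 assessment the rating can come before the second infusion, so it may be reverse causation.

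The plan has no safeguard against this. Section 9.9.2 discusses confounding only in general terms, and the ENCePP checklist (item 10.5) marks analytic control of confounding as not applicable. The report goes to the regulator, and sections 4 and 7 say the surveillance results are reflected in the approved information. A described meaning for a dose covariate could suggest that more exposure goes with less effectiveness when the data show only who was re-infused.

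**Working it through.** **Plan's own figure.** There is none to reproduce. The 21 patients in 9.5 come from prevalence and market conditions, and no effect size, power or precision is stated.

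**Inputs from the protocol.** n = 21; a second infusion only if symptoms persist at 1 week; effective or not as the outcome.

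**Assumed inputs (not in the protocol).**
- p = share responding by Week 1: 0.4, 0.6, 0.7
- q = share of the others who are re-infused: 0.5, 0.7, 0.9
- Week 4 effective rate: 0.9 in Week 1 responders; 0.4 in the others after one infusion
- r = Week 4 effective rate in the others after two infusions: 0.4 (no effect, true OR 1) or 0.6 (benefit, true OR (0.6/0.4)/(0.4/0.6) = 2.25)

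**Crude Week 4 odds ratio.** The one-infusion group mixes responders with the patients who persisted but were not re-infused:

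R1 = [0.9p + 0.4(1−p)(1−q)] / [p + (1−p)(1−q)]

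crude OR = [r/(1−r)] / [R1/(1−R1)]

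The middle setting and the two that bound the ranges:

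| p | q | R1 | odds of R1 | crude OR, true OR 1 | crude OR, true OR 2.25 |
|---|---|---|---|---|---|
| 0.4 | 0.5 | (0.36+0.12)/0.70 = 0.686 | 2.18 | 0.667/2.18 = 0.31 | 1.5/2.18 = 0.69 |
| 0.6 | 0.7 | (0.54+0.048)/0.72 = 0.817 | 4.45 | 0.667/4.45 = 0.15 | 1.5/4.45 = 0.34 |
| 0.7 | 0.9 | (0.63+0.012)/0.73 = 0.880 | 7.30 | 0.667/7.30 = 0.09 | 1.5/7.30 = 0.21 |

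**How often it would be significant.** Studies of 21 patients were simulated over the nine settings, with a two-sided Fisher test at 0.05 of one against two infusions. With no effect, the result is significant against two infusions in about 15–50% of studies. With a true OR of 2.25, it is significant in the wrong direction in about 3–21%.

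**Limit of the reversal.** If the second infusion raised the rate from 40% to 90% (r = 0.9, odds 9), the crude OR would run from 9/7.30 = 1.2 to 9/2.18 = 4.1. The true OR is 9/0.667 = 13.5, so the estimate is still biased downwards but not reversed.

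**Wider check.** A second grid had 45 scenarios in which the second infusion always helps: Week 1 responders 30–70%, re-infusion 50–100%, true OR 1.56–9.0. The crude OR was below the true OR in all 45. It was below 1 in 35, about 1.0 in 1 and above 1 in 9.

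**Week 1 outcome.** If every re-infused patient were rated ineffective, 0 of 5 against 10 of 16 effective gives Fisher p = 0.035 with no dose effect at all. That is an extreme case. Suppose instead that all patients without persisting symptoms are rated effective and 80% of those with persisting symptoms are still rated improved. The significant share is then about 5–14% over the same p and q; at 60% it is about 13–48%.

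**The case against.** **The link from dose to model is inferred.** Section 9.7.3 names no covariates, and full details are left to the SAP. This stands as a limit on certainty: reading 9.3.3 as the source of the factors in 9.7.3 is natural, not explicit. It does not dissolve the point. The protocol itself lists the dose variables as covariates and requires significant covariates to be interpreted, with no restriction to baseline.

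**A stronger reading is tempting: that a second infusion must appear to cause failure whatever the drug does.** The documents do not support it. The bias runs against the second infusion under the assumed structure, but reversal depends on the size of the benefit and the share re-infused. A significant reversal with 21 patients is usually the minority result.

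**A reader might also infer that the two-infusion group has a Week 1 effective rate of zero by construction.** It does not. *Improved* in 9.3.2.3 covers any effect of maintaining or improving symptoms, so a patient with persisting symptoms can be re-infused and still be rated effective.

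**The safety models.** Section 9.7.2 names no dose variable. If one were used, two distortions would pull in different directions: events before the second infusion would count under two infusions, while a patient with an early reaction might never receive a second. No net direction or size can be shown, so for safety this is only a precaution.

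**Limited consequence.** All analyses are exploratory, effectiveness is secondary, and the overall assessment is a further outcome. This lowers the stakes, but the exploratory label does not correct a bias whose direction is known.

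**Conclusion.** The point holds for the effective-rate models. Total dose, duration and average daily dose are determined after baseline and partly by early response, and the plan allows them to be fitted and interpreted as influences on that response. The bias is against the second infusion. Under the assumed rates, the crude Week 4 OR is 0.09–0.31 in place of 1, and 0.21–0.69 in place of 2.25. Those sizes rest wholly on the assumed response and re-infusion rates. They also assume that no one responding by Week 1 is re-infused, and that the model does not condition on Week 1 status. The certainty of a reversed or significant finding is not established, and no size is claimed for Week 1 or for adverse events.

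**What to change.** In 9.3.3(2) and 9.7.3, restrict the factor models for the effective rate to baseline covariates, and state that total administered dose, duration and average daily dose are not explanatory variables in them. Keep these variables as descriptions of exposure. Report the second infusion descriptively: number and percentage re-infused, with GPPGA at Week 1 and outcome at Week 4. Apply the same baseline-only rule to the adverse event models in 9.7.2, and describe adverse events by the number of infusions received before onset.

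A comparison confined to patients with persisting symptoms at Week 1 removes the main source of bias in principle, but it is too small to estimate. With half responding by Week 1 and 80% of the others re-infused, it leaves 21 × 0.5 × 0.8 ≈ 8 against 21 × 0.5 × 0.2 ≈ 2 patients.

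The cost is wording in the protocol, carried into the SAP. Administration dates, Week 1 scores and event onset dates are already collected. The downside is that no odds ratio for dose is reported. No change to dosing is proposed.
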